APPENDIX 3 RECIST 1.1

Changes in tumor measurements and tumor responses will be assessed by the investigator using the RECIST 1.1 (Response Evaluation Criteria in Solid Tumors) criteria. (Eisenhauer, et al 2009.)

Source: Eisenhauer et al New response evaluation criteria in solid tumours: Revised RECIST guideline (version 1.1), European Journal of Cancer, 2009, Vol. 45, p 228-247

1 **ASSESSMENT OF OVERALL TUMOR BURDEN AND MEASURABLE DISEASE**

To assess objective response or future progression, it is necessary to estimate the *overall tumor burden at baseline* and use this as a comparator for subsequent measurements. Measurable disease is defined by the presence of at least one measurable tumor lesion. When CT scans have slice thickness greater than 5 mm, the minimum size for a measurable lesion should be twice the slice thickness.

At baseline, tumor lesions/lymph nodes will be categorized measurable or non-measurable as follows:

1.1 **Measurable lesions**

Measurable lesions must be accurately measured in at least one dimension (longest diameter in the plane of the measurement to be recorded) with a minimum size of:

- 10 mm by CT/MRI scan - (CT/MRI scan slice thickness no greater than 5 mm)
- 10 mm caliper measurement by clinical exam (lesions which cannot be accurately measured with calipers should be recorded as non-measurable)
- 20 mm by chest x-ray
- *Malignant lymph nodes*: To be considered pathologically enlarged *and* measurable, a lymph node must be ≥ 15 mm in *short* axis when assessed by CT scan (CT scan slice thickness recommended to be no greater than 5 mm). At baseline and in follow-up, only the *short* axis will be measured and followed.

1.2 **Non-measurable lesions**

- All other lesions, including small lesions (longest diameter < 10 mm or pathological lymph nodes with ≥ 10 to < 15 mm short axis), as well as truly non-measurable lesions.
- Lesions considered truly non-measurable include: leptomeningeal disease, ascites, pleural or pericardial effusion, inflammatory breast disease, lymphangitic involvement of skin or lung, abdominal masses/abdominal organomegaly identified by physical exam that in not measurable by reproducible imaging techniques.

1.3 Special considerations regarding lesion measurability

1.3.1 Bone lesions

- Bone scan, PET scan or plain films are *not* considered adequate imaging techniques to measure bone lesions. However, these techniques can be used to confirm the presence or disappearance of bone lesions.
- Lytic bone lesions or mixed lytic-blastic lesions, with *identifiable soft tissue components*, that can be evaluated by cross sectional imaging techniques such as CT or MRI can be considered as measurable lesions if the *soft tissue component* meets the definition of measurability described above.
- Blastic bone lesions are non-measurable.

1.3.2 Cystic lesions

- Lesions that meet the criteria for radiographically defined simple cysts should not be considered as malignant lesions (neither measurable nor non-measurable) since they are, by definition, simple cysts.
- ‘Cystic lesions’ thought to represent cystic metastases can be considered as measurable lesions, if they meet the definition of measurability described above. However, if non-cystic lesions are present in the same subject, these are preferred for selection as target lesions.

1.3.3 Lesions with prior local treatment

Tumor lesions situated in a previously irradiated area, or in an area subjected to other loco-regional therapy, are usually not considered measurable unless there has been demonstrated progression in the lesion.

1.4 Specifications by methods of measurements

1.4.1 Measurement of lesions

All measurements should be recorded in metric notation (mm). All baseline evaluations should be performed as close as possible to the treatment start and never more than 28 days before the beginning of the treatment.

1.4.2 Method of assessment

The **same method of assessment and the same technique should be used** to characterize each identified and reported lesion at baseline and during follow-up. Imaging based evaluation should always be done rather than clinical examination unless the lesion(s) being followed cannot be imaged but are assessable by clinical exam.

1.4.2.1 CT/MRI scan

CT/MRI is the best currently available and reproducible method to measure lesions selected for response assessment. Measurability of lesions on CT/MRI scan is based on the assumption that CT/MRI slice thickness is 5 mm or less. When CT scans have slice thickness greater than 5 mm, the minimum size for a measurable lesion should be twice the slice thickness.

1.4.2.2 Chest X-ray

Chest CT is preferred over chest X-ray, particularly when progression is an important endpoint, since CT is more sensitive than X-ray, particularly in identifying new lesions. However, lesions on chest X-ray may be considered measurable if they are clearly defined and surrounded by aerated lung.

1.4.2.3 Clinical lesions

Clinical lesions will only be considered measurable when they are superficial and ≥ 10 mm diameter as assessed using calipers. For the case of skin lesions, documentation by color photography including a ruler to estimate the size of the lesion is suggested. As previously noted, when lesions can be evaluated by both clinical exam and imaging, imaging evaluation should be undertaken since it is more objective and may also be reviewed at the end of the study.

1.4.2.4 Ultrasound

Ultrasound is *not* useful in assessment of lesion size and should not be used as a method of measurement. If new lesions are identified by ultrasound in the course of the study, confirmation by CT or MRI is advised.

1.4.2.5 Endoscopy, laparoscopy

The utilization of these techniques for objective tumor evaluation is *not* advised.

1.4.2.6 Tumor markers

Tumor markers *alone* cannot be used to assess objective tumor response.

2 BASELINE DOCUMENTATION OF 'TARGET' AND 'NON-TARGET' LESIONS

2.1 Target lesions

When more than one measurable lesion is present at baseline all lesions up to **a maximum of five lesions total (and a maximum of two lesions per organ) representative of all involved organs should be identified as target lesions** and will be recorded and measured at baseline.

Target lesions should be selected on the basis of their **size** (lesions with the longest diameter), be representative of all involved organs, and should lend themselves to **reproducible repeated measurements**.

A **sum of the diameters** (longest for non-nodal lesions, short axis for nodal lesions) for all target lesions will be calculated and reported as the **baseline sum diameters**. If lymph nodes are to be included in the sum, then as noted below, only the **short axis** is added into the sum. The baseline sum diameters will be used as reference to further characterize any objective tumor regression in the measurable dimension of the disease.

2.1.1 Lymph nodes

Lymph nodes merit special mention since they are normal anatomical structures which may be visible by imaging even if not involved by tumor. Pathological nodes which are defined as measurable and may be identified as target lesions must meet the criterion of a **short axis of**

≥ 15 mm by CT scan. Only the *short* axis of these nodes will contribute to the baseline sum. Nodes that have a short axis < 10 mm are considered non-pathological and should not be recorded or followed.

2.2 Non-target lesions

All other lesions (or sites of disease) including pathological lymph nodes should be identified as *non-target lesions* and should also be recorded at baseline. Measurements are not required and these lesions should be followed as ‘present’, ‘absent’, or in rare cases ‘unequivocal progression’. In addition, it is possible to record multiple non-target lesions involving the same organ as a single item on the case record form (eg, ‘multiple enlarged pelvic lymph nodes’ or ‘multiple liver metastases’).

3 TUMOR RESPONSE EVALUATION

3.1 Evaluation of target lesions

Complete Response (CR): **Disappearance of all target lesions.** Any pathological lymph nodes (whether target or non-target) must have reduction in short axis to < 10 mm.

Partial Response (PR): At least a **30% decrease in the sum of diameters of target lesions**, taking as reference the baseline sum diameters.

Progressive Disease (PD): At least a **20% increase in the sum of diameters of target lesions, taking as reference the *smallest sum on study*** (this includes the baseline sum if that is the smallest on study). In addition to the relative increase of 20%, the sum must also demonstrate an **absolute increase of at least 5 mm**. (*Note*: the appearance of one or more new lesions is also considered progression).

Stable Disease (SD): Neither sufficient shrinkage to qualify for PR nor sufficient increase to qualify for PD, taking as reference the smallest sum diameters while on study.

3.1.1 Special notes on the assessment of target lesions

3.1.1.1 Lymph nodes

Lymph nodes merit special mention since they are normal anatomical structures which may be visible by imaging even if not involved by tumor. Pathological nodes which are defined as measurable and may be identified as target lesions must meet the criterion of a **short axis of ≥ 15 mm by CT scan**. Only the *short* axis of these nodes will contribute to the baseline sum. Nodes that have a short axis < 10 mm are considered non-pathological and should not be recorded or followed.

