3.1.1 Special notes on the assessment of target lesions

3.1.1.1 Lymph nodes

Lymph nodes merit special mention since they are normal anatomical structures which may be visible by imaging even if not involved by tumor. Pathological nodes which are defined as measurable and may be identified as target lesions must meet the criterion of a **short axis of ≥ 15 mm by CT scan**. Only the *short* axis of these nodes will contribute to the baseline sum. Nodes that have a short axis <10 mm are considered non-pathological and should not be recorded or followed.

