3.1.1.2 Target lesions that become ‘too small to measure’

All lesions (nodal and non-nodal) recorded at baseline should have their actual measurements recorded at each subsequent evaluation, even when very small (eg, 2 mm). If the radiologist is able to provide an actual measurement, that should be recorded, even if it is below 5 mm.

However, when such a lesion becomes difficult to assign an exact measure to then:

- if it is the opinion of the radiologist that the lesion has likely disappeared, the measurement should be recorded as 0 mm.
- if the lesion is believed to be present and is faintly seen but too small to measure, a default value of 5 mm should be assigned (note: in case of a lymph node believed to be present and faintly seen but too small to measure, a default value of 5 mm should be assigned in this circumstance as well). This default value is derived from the 5 mm CT slice thickness (but should not be changed with varying CT slice thickness).

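### Appendix 3, section 3.1.1.1 repeats a baseline rule on nodes under 10 mm within on-study assessment, where it contradicts the rule that target nodes stay measured

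*Protocol*

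**What the plan says.** Appendix 3 appears in both revisions in the protocol file (07d and 08), with the same conflict in each.

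- **Section 2.1.1 (baseline documentation)** sets the size limits for choosing nodes and ends with the instruction not to record or follow nodes under 10 mm.
- **Section 3.1.1.1 (special notes on assessing target lesions, under tumor response evaluation)** repeats that paragraph. It requires a target node to have a "short axis of ≥ 15 mm by CT scan" and then says "Nodes that have a short axis < 10 mm are considered non-pathological and should not be recorded or followed". Revised Protocol 07d has the same sentence: "Nodes that have a short axis <10 mm are considered non-pathological and should not be recorded or followed". Neither limits it to baseline.
- **Section 3.1.1.2** says: "All lesions (nodal and non-nodal) recorded at baseline should have their actual measurements recorded at each subsequent evaluation, even when very small". It gives 2 mm as an example, allows 0 mm when the radiologist thinks the lesion has likely disappeared, and assigns 5 mm to a node that is faintly seen but too small to measure.
- **Section 1.1** says that, at baseline and in follow-up, only a node's short "axis will be measured and followed".
- **Section 3.1, complete response:** "Any pathological lymph nodes (whether target or non-target) must have reduction in short axis to < 10 mm".

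**The concern.** Partial response (PR) is at least a "30% decrease in the sum of diameters of target lesions" from the baseline sum. Progression (PD) is an increase of at least 20% and at least 5 mm over the smallest sum on study. If a node leaves the sum when it falls below 10 mm, the follow-up sum loses up to 9 mm while the baseline sum still carries that node's 15 mm or more. The nadir is also set too low, so the sum jumps when the node returns to 10 mm.

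This sum feeds best overall response, and so ORR (the primary endpoint), duration of response, progression-free survival and, in the two-stage cohorts, the Stage 1 gate of 2 responders in 18. Investigators apply the appendix themselves, and central review covers only selected tumor types. Two sites reading different paragraphs could classify the same scan differently.

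**Working it through.** **Step 1. Can the sentence in 3.1.1.1 apply to a target node?** A target node is at least 15 mm at baseline. In a section on assessing target lesions, a rule for nodes under 10 mm can therefore reach a target node only after it has shrunk. Section 3.1.1.2 requires the measurement to continue at exactly that point.

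**Step 2. What follows if 3.1.1.1 is applied literally?** There are two routes.

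*Route A: the node is left blank.* Section 4.1.1 makes a time point not evaluable (NE) when only some lesions are measured, unless a convincing argument shows that the missing lesion would not change the response. Table 1 in section 4.1 also gives NE when not all target lesions are evaluated and non-target disease has not progressed. If this happens at the scan that would have confirmed a real PR, Table 3 in section 4.2 turns PR followed by NE into stable disease (SD) or NE.

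*Route B: the node is treated as gone and drops out of the sum.* Illustrative sizes (assumed): node 20 mm + liver 40 mm, so the baseline sum is 60 mm.

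| Scan | Node kept (3.1.1.2) | Node dropped (3.1.1.1) |
|---|---|---|
| Node 9, liver 38 | 47/60 − 1 = −21.7%, SD | 38/60 − 1 = −36.7%, PR |
| Node 10, liver 38 | 48/47 − 1 = +2.1%, +1 mm, not PD | 48/38 − 1 = +26.3%, +10 mm, PD |

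**Step 3. How special is the example?** Let *n* be the baseline node and *o* the other target disease, in mm, with *o* unchanged. The node falls to 9 mm and then regrows to 10 mm.

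- Dropped sum reads as PR: *o* ≤ 0.7(*n* + *o*), that is *o* ≤ 7*n*/3.
- Kept sum is still SD: *o* + 9 > 0.7(*n* + *o*), that is *o* > 7*n*/3 − 30.
- False PD on re-entry: 10 ≥ 0.2*o*, that is *o* ≤ 50.

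On a grid of whole millimetres from 10 to 150 mm of other disease:

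| Node at baseline | False PR | False PR, then false PD |
|---|---|---|
| 15 mm | 10–35 mm | 10–35 mm |
| 20 mm | 17–46 mm | 17–46 mm |
| 30 mm | 41–70 mm | 41–50 mm |

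The false PR disappears just outside these limits. With a 15 mm node and 36 mm of other disease, the dropped sum is 36/51 − 1 = −29.4%, still SD.

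**Step 4. Does it reach the endpoint?** Section 4.1.2 requires a response to be met again at least 4 weeks later. A false PR enters ORR only if the node is left out at that scan too. A node that stays under 10 mm would be left out again by an assessor who applies the same reading.

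**The case against.** The strongest reply is that the appendix, read as a whole, answers the question. Section 3.1.1.2 comes next, names nodal lesions expressly and is the more specific rule. Section 1.1 and the complete-response rule presuppose measurement below 10 mm. The paragraph in 3.1.1.1 itself speaks of selecting nodes and of the baseline sum, so it reads like misplaced baseline text. A careful assessor would keep measuring. All of this stands, and it shows which text should be corrected. It does not remove the contradiction, because the sentence has no baseline limit and nothing states which section governs.

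The second reply is that a reader might infer that 3.1.1.1 makes stable disease into a confirmed PR as a matter of course. The protocol does not support that. An unrecorded node is not 0 mm: section 3.1.1.2 reserves 0 mm for a lesion judged likely to have disappeared, and section 4.1.1 normally makes the time point NE. A false PR needs an assessor to depart from both, and to do so again at the confirming scan. This also stands. The false PR and false PD are possible outcomes, not prescribed ones.

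The reach is also limited. The Stage 1 gate does not apply to the one-stage bladder, ovarian and additional pancreatic cohorts, and the small cell lung cancer arms had already passed it. The primary ORR of the small cell lung cancer expansion is by central review under an imaging charter that is not shown. Sites also receive an imaging manual and a RECIST pocket guide.

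**Conclusion.** The point holds as a contradiction within the response criteria that define ORR, duration of response and progression-free survival. Both revisions carry it. The sentence is wrong where it stands in 3.1.1.1, and the rest of the appendix supports 3.1.1.2.

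For a single subject, the literal reading costs either an evaluable time point or 9 mm of the sum for a node at 9 mm. Those 9 mm are 22.5 percentage points of apparent shrinkage at a 40 mm baseline sum, 15 at 60 mm and 9 at 100 mm. That is enough to change the category within the ranges shown, which rest on assumed lesion sizes and unchanged non-nodal disease. The error can go either way: a dropped node can create a PR, and a blank can lose one.

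A reader might infer a definite inflation of ORR, or a definite rise in the chance that an inactive arm passes the 2-of-18 gate. The protocol does not give the share of subjects with target nodes, how many of those nodes fall below 10 mm, or how assessors handled them. Any such figure would be an assumed input, so the effect on ORR stays unquantified. The correction is worth making because the conflict is certain and the repair is small.

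**What to change.** In both revisions of Appendix 3, keep the sentence about nodes under 10 mm in section 2.1.1 only. In section 3.1.1.1 state instead that a node selected as a target lesion keeps its actual short-axis measurement in the sum at every assessment, including below 10 mm, as 3.1.1.2 already requires.

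Query target nodes that, after falling below 10 mm, were left blank or were set to 0 mm without a radiologist's judgement that the lesion had disappeared. Leave valid zeros and the 5 mm default untouched, since 3.1.1.2 provides for both. Where the query changes a measurement, rederive the sum and the time-point response.

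The cost is one changed sentence per revision and one data query. Design, sample size and treatment do not change. Reported ORR could move slightly in either direction.

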3.1.1.2 Target lesions that become ‘too small to measure’

All lesions (nodal and non-nodal) recorded at baseline should have their actual measurements recorded at each subsequent evaluation, even when very small (eg, 2 mm). If the radiologist is able to provide an actual measurement, that should be recorded, even if it is below 5 mm.

However, when such a lesion becomes difficult to assign an exact measure to then:

- if it is the opinion of the radiologist that the lesion has likely disappeared, the measurement should be recorded as 0 mm.
- if the lesion is believed to be present and is faintly seen but too small to measure, a default value of 5 mm should be assigned (note: in case of a lymph node believed to be present and faintly seen but too small to measure, a default value of 5 mm should be assigned in this circumstance as well). This default value is derived from the 5 mm CT slice thickness (but should not be changed with varying CT slice thickness).

3.1.1.3 Target lesions that split or coalesce on treatment

- When non-nodal lesions ‘fragment’, the longest diameters of the fragmented portions should be added together to calculate the target lesion sum.
- As lesions coalesce, a plane between them may be maintained that would aid in obtaining maximal diameter measurements of each individual lesion. If the lesions have truly coalesced such that they are no longer separable, the vector of the longest diameter in this instance should be the maximal longest diameter for the ‘coalesced lesion’.

3.2 Evaluation of non-target lesions

While some non-target lesions may actually be measurable, they need not be measured and instead should be assessed only qualitatively at the time points specified in the protocol.

Complete Response (CR): Disappearance of all non-target lesions and normalization of tumor marker level. All lymph nodes must be non-pathological in size (< 10 mm short axis).

Non-CR/Non-PD: Persistence of one or more non-target lesion(s) and/or maintenance of tumor marker level above the normal limits.

Progressive Disease (PD): *Unequivocal progression* of existing non-target lesions. (*Note*: the appearance of one or more new lesions is also considered progression).

3.2.1 Special notes on assessment of non-target lesions

The concept of progression of non-target disease requires additional explanation as follows:

3.2.1.1 When the subject also has measurable disease

- To achieve ‘unequivocal progression’ on the basis of the non-target disease, there must be an overall level of substantial worsening in non-target disease such that, even in presence of SD or PR in target disease, the overall tumor burden has increased sufficiently to merit discontinuation of therapy.
- A modest ‘increase’ in the size of one or more non-target lesions is usually not sufficient to qualify for unequivocal progression status.

3.2.1.2 When the subject has only non-measurable disease

- To achieve ‘unequivocal progression’ on the basis of the non-target disease, there must be an overall level of substantial worsening such that the overall tumor burden has increased sufficiently to merit discontinuation of therapy.
- A modest ‘increase’ in the size of one or more non-target lesions is usually not sufficient to qualify for unequivocal progression status.
- Because worsening in non-target disease cannot be easily quantified (by definition: if all lesions are non-measurable) a useful test that can be applied when assessing subjects for unequivocal progression is to consider if the increase in overall disease burden based on the change in non-measurable disease is comparable in magnitude to the increase that would be required to declare PD for measurable disease: ie, an increase in tumor burden representing an additional 73% increase in ‘volume’ (which is equivalent to a 20% increase diameter in a measurable lesion). Examples include an increase in a pleural effusion from ‘trace’ to ‘large’, an increase in lymphangitic disease from localized to widespread, or may be described in protocols as ‘sufficient to require a change in therapy’.
- If ‘unequivocal progression’ is seen, the subject should be considered to have had overall PD at that point.

3.2.1.3 Tumor markers

Tumor markers *alone* cannot be used to assess objective tumor responses. If markers are initially above the upper normal limit, however, they must normalize in order for a subject to be considered as having attained a complete response.

3.3 New lesions

The appearance of new malignant lesions denotes disease progression. The finding of a new lesion should be unequivocal: ie, not attributable to differences in scanning technique, change in imaging modality or findings thought to represent something other than tumor (for example, some ‘new’ bone lesions may be simply healing or flare of pre-existing lesions). This is particularly important when the subject’s baseline lesions show partial or complete response. For example, necrosis of a liver lesion may be reported on a CT scan report as a ‘new’ cystic lesion, which it is not.

A lesion identified on a follow-up study in an anatomical location that was *not* scanned at baseline is considered a new lesion and will indicate disease progression. An example of this is the subject who has visceral disease at baseline and while on study has a CT or MRI brain scan ordered which reveals metastases. The subject’s brain metastases are considered to be evidence of PD even if he/she did not have brain imaging at baseline.

If a new lesion is equivocal, for example because of its small size, continued therapy and follow-up evaluation will clarify if it represents truly new disease. *If repeat scans confirm there is definitely a new lesion, then progression should be declared using the date of the initial scan.*

3.3.1 **FDG-PET evaluation**

While FDG-PET response assessments need additional study, it is sometimes reasonable to incorporate the use of the qualitative assessment of FDG-PET scanning to complement CT scanning in assessment of progression (particularly possible ‘new’ disease). New lesions on the basis of FDG-PET imaging can be identified according to the following algorithm:

- Negative FDG-PET at baseline, with a positive FDG-PET at follow-up might be a sign of PD based on a new lesion. However, other reasons for newly detected lesions with increased FDG-PET uptake, such as inflammatory lymphnodes, should be taken into consideration.
- No FDG-PET at baseline and a positive FDG-PET at follow-up:
 - If the positive FDG-PET at follow-up corresponds to a new site of disease confirmed by CT, this is PD.
 - If the positive FDG-PET at follow-up is not confirmed as a new site of disease on CT, additional follow-up CT scans are needed to determine if there is truly progression occurring at that site (if so, the date of PD will be the date of the initial positive FDG-PET scan).
 - If the positive FDG-PET at follow-up corresponds to a pre-existing site of disease on CT that is not progressing on the basis of the anatomic images, this is not PD.
 - Other reasons for newly detected lesions with increased FDG-PET uptake, such as inflammatory lymphnodes, should be taken into consideration.

4 **RESPONSE CRITERIA**

4.1 **Time point response**

A response assessment should occur at each time point specified in the protocol.

For subjects who have **measurable disease** at baseline Table 1 provides a summary of the overall response status calculation at each time point.

Table 1: Time point response: subjects with target (+/- non-target) disease.			
Target lesions	Non-target lesions	New lesions	Overall response
CR	CR	No	CR
CR	Non-CR/non-PD	No	PR
CR	Not evaluated	No	PR
PR	Non-PD or not all evaluated	No	PR

Table 1: Time point response: subjects with target (+/- non-target) disease.			
Target lesions	Non-target lesions	New lesions	Overall response
SD	Non-PD or not all evaluated	No	SD
Not all evaluated	Non-PD	No	NE
PD	Any	Yes or No	PD
Any	PD	Yes or No	PD
Any	Any	Yes	PD

CR = complete response, PR = partial response, SD = stable disease, PD = progressive disease, NE = not evaluable

For subjects who have **non-measurable** (therefore non-target) disease only, Table 2 is to be used.

Table 2: Time point response: Subjects with non-target disease only		
Non-target lesions	New lesions	Overall response
CR	No	CR
Non-CR/non-PD	No	Non-CR/non-PD ^a
Not all evaluated	No	NE
Unequivocal PD	Yes or No	PD
Any	Yes	PD

^a 'Non-CR/non-PD' is preferred over 'stable disease' for non-target disease since SD is increasingly used as endpoint for assessment of efficacy in some trials so to assign this category when no lesions can be measured is not advised.

CR = complete response, PD = progressive disease, and NE = not evaluable.

